
DOSE ESCALATION PART

Regimen description:

Concomitant treatment by continuous Olaparib and radiotherapy.

- Olaparib will be given orally, continuously, twice a day, as appropriate for assigned dose level, from Day1 to the end of radiotherapy. Olaparib will be started one week before the start of radiotherapy and will be continued until the last day of radiotherapy. Beyond this period, Olaparib could be continued at the investigator's discretion and after sponsor authorization, until progression.
- Radiotherapy consists of fractionated focal irradiation at a dose of 1.8 Grays (Gy) per fraction given once daily five days per week (Monday through Friday), for a total dose of 59.4 Gy (ie. 33 fractions). Radiotherapy starts at D8.

Dose levels

- Dose escalation study assessing 4 doses level of Olaparib in association with

Level	-1	1	2	3	4
Olaparib	25 mg (daily)	25 mg (b.i.d)	50 mg (b.i.d)	100 mg (b.i.d)	150 mg (b.i.d)

concomitant radiotherapy.

- The starting dose of Olaparib is 25 mg b.i.d.
- The maximum dose of Olaparib administered (150 mg x 2) will not be exceeded.
- No skipping of the dose will be allowed.
- For a given patient, dose will never be escalated.
- **As long as no DLT is observed** patients will be allocated to 4 dose levels following a 3+3 design with the following characteristics:
 - Inclusions of cohorts of 3 patients,
 - At dose levels 1 and 2, before accrual to next higher dose level, at least 2 patients with 6-week follow-up will be required,
 - At dose level 3, before accrual to dose level 4, at least 2 patients with 8-week follow-up will be required
- **As soon as the first DLT is observed**, patients will be allocated following a TITE-CRM design [Normolle et al. Statistics in Medicine 2003]. When a patient is eligible for enrollment, the probability of DLT is estimated for each dose level, based on the trial experience up to that time and the prior expectations for toxicity.
 - Each new patient is assigned to the currently estimated target dose, defined as the dose having an estimated probability of toxicity closest to but not greater than the target rate (33%), subject to the following restrictions :
 - A minimum of 2 patients will be entered on each dose level,
 - At dose levels 1 and 2, before accrual to next higher dose level, at least 2 patients with 6-week follow-up will be required,
 - At dose level 3, before accrual to next higher dose level, at least 2 patients with 8-week follow-up will be required,

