10.3. STATISTICAL ANALYSIS

A statistical Analysis Plan (SAP) will be produced by the statistician of the study and validated by the steering committee. A preliminary version will be produced prior to the first inclusion. The SAP will be updated when necessary (Substantial modification of the protocol, IDMC recommendations, etc) and systematically validated by the steering committee.

Dose escalation part

- Dose-toxicity modeling
 - At the end of the trial, the posterior distribution of the dose-toxicity parameter α and DLT at each dose, will be estimated using the power dose-toxicity model and normal prior distribution on α used to conduct the trial.
 - 95% posterior intervals for the toxicity probabilities will be reported.
- Patient characteristics at baseline will be provided
 - Compliance with eligibility criteria,
 - Epidemiological characteristics,
 - Clinical and laboratory characteristics,
 - Treatment characteristics.
- Toxicities observed at each dose level will be recorded in terms of event type, severity, dates of beginning and end, reversibility and evolution. Data will be gathered in tables summarizing toxicities.
- Efficacy analysis: efficacy endpoints will be reported in terms of counts and proportions for each dose levels. Subgroup analyses will be conducted for metastatic and non-metastatic patients.
- All analyses will be descriptive; no p-values will be calculated.
- Data analyses will be provided by dose groups and for all study patients, combined wherever appropriate.
- For continuous variables, summary statistics will include number of patients, median, minimum, and maximum, and additional percentiles if appropriate.
- Categorical endpoints will be summarized using number of patients, frequency, percentages.
- For survival endpoints, median survival time will be reported.
- Missing data will not be imputed.

Expansion cohort

- Patient characteristics at baseline will be provided
 - Compliance with eligibility criteria,
 - Epidemiological characteristics,
 - Clinical and laboratory characteristics,
 - Treatment characteristics.
- Toxicities will be recorded in terms of event type, severity, dates of beginning and end, reversibility and evolution. Data will be gathered in tables summarizing toxicities and side effects for each dose level and cycle.
- Efficacy analysis: efficacy endpoints will be reported in terms of counts and proportions. Subgroup analyses will be conducted for metastatic and non-metastatic patients.

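### The switch to the TITE-CRM at the first DLT has no coherence restriction, so under some priors the model can assign the next patient to a higher dose level directly after a DLT

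*Protocol*

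**What the plan says.** The protocol synopsis (Dose escalation part, Dose levels) and section 3.4.2 describe two stages.

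- **Before any DLT:** "Inclusions of cohorts of 3 patients", with escalation governed by follow-up and no model.
- **From the first DLT:** "patients will be allocated following a TITE-CRM design". Each new patient receives the dose whose estimated DLT probability is "closest to but not greater than the target rate (33%), subject to the following restrictions".

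Four such conditions are then listed:

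- every level must receive no fewer than 2 patients;
- levels 1 and 2 each need two patients followed for 6 weeks before the level above is opened to accrual;
- level 3 needs two patients followed for 8 weeks before level 4 is opened;
- the sponsor may suspend inclusions if accrual is fast.

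The same sections also state "No skipping of the dose will be allowed", rule out raising the dose within a patient, and cap the dose at level 4. The DLT validation committee (section 12.1.2: an investigator, a statistician and a pharmacist) is to be consulted before a new dose level is opened for the first time.

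Section 10.3 says that the final analysis reuses the trial's own model, "using the power dose-toxicity model and normal prior distribution". The skeleton and prior variance appear nowhere. The prior is to be chosen to control the expected number of toxicities over several scenarios. The SAP contains no TITE-CRM text. Its synopsis still describes a 3+3 design.

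**The concern.** A dose-finding rule is called coherent if it never raises the dose for the next patient in direct response to a DLT. If a CRM chooses every dose from the first patient on, this is close to automatic: a DLT raises every estimated probability, and only follow-up gained meanwhile on other patients can offset it.

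The two-stage rule loses that property at the switch. In the first stage the dose climbs by cohort whatever a model would say, so the current level may lie below the one the model would recommend. When the first DLT starts the model, its first recommendation need not agree with the current level and can be higher.

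The written restrictions limit or delay that step without forbidding it. No skipping limits it to one level. The ban on raising a patient's own dose does not concern the next patient. The minimum of 2 patients and the 6- or 8-week conditions are met once two patients at the level have that follow-up. At stake is the exposure of one patient to a higher dose just after a warning.

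**Working it through.** **Stated figures.** The dose escalation size reproduces: 6 × 4 levels = 24. So does the DLT window: 1 + 6.5 + 6 = 13.5 weeks. The weights at the two follow-up conditions are 6/13.5 = 0.444 and 8/13.5 = 0.593. The documents give no operating characteristics for the TITE-CRM, so no stated figure tests this point directly.

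**Model.** From the protocol: power model, normal prior, weight = follow-up/13.5, target 0.33, highest level with estimate not above 0.33. Assumed: the skeleton s, the prior variance, and use of the posterior mean as plug-in estimate.

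- p_i(a) = s_i^exp(a), with a ~ N(0, 1.34).
- A patient with a DLT contributes p_i(a) to the likelihood. A patient without one contributes 1 − w·p_i(a).
- The estimate at level i is s_i^exp(â), where â is the posterior mean of a.

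**Worked example.** Skeleton 0.147/0.233/0.33/0.431 (prior MTD at level 3, indifference half-width 0.05). Patients at lower levels are DLT-free and fully followed. The current level has 1 DLT in 3.

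| Data | Other two patients at current level | â | Estimates, levels 1–4 | Next level |
|---|---|---|---|---|
| 0/3, 0/3, 1/3 | full follow-up | 0.422 | 0.05/0.11/0.18/0.28 | 4 |
| 0/3, 0/3, 1/3 | 8 weeks | 0.343 | 0.07/0.13/0.21/0.31 | 4 |
| 0/3, 1/3 | full follow-up | 0.054 | 0.13/0.21/0.31/0.41 | 3 |
| 0/3, 1/3 | 6 weeks | −0.108 | 0.18/0.27/0.37/0.47 | 2 (stays) |

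For the first row, exp(0.422) = 1.525 and 0.431^1.525 = 0.28, which is below 0.33, so level 4 is assigned.

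**Fifteen calibrations.** Prior MTD at level 2, 3 or 4; half-width 0.04, 0.05, 0.06, 0.07 or 0.08; variance 1.34. Number that escalate after 1/3:

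| Current level | Minimum follow-up | Full follow-up |
|---|---|---|
| 1 | 0 of 15 | 0 of 15 |
| 2 | 1 of 15 | 8 of 15 |
| 3 | 7 of 15 | 10 of 15 |

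No calibration with half-width 0.08 escalates in any of these cases.

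**Wider grid.** Sixty-four priors: prior MTD at levels 1 to 4; half-width 0.04, 0.06, 0.08 or 0.10; prior SD 0.5, 0.75, 1.16 or 2. From minimum to full follow-up, the model escalates after 1/3 in 7 to 12 of 64 at level 1, 7 to 22 at level 2 and 18 to 23 at level 3.

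**Simulation.** 1000 trials of 24 patients per cell, half-width 0.06, uniform DLT times. Accrual follows the planned pace: 56 × 4.345/41 = one patient per 5.9 weeks. The table gives the percentage of trials with at least one escalation directly after a DLT. The assumed true curves are A 0.05/0.10/0.20/0.33, B 0.10/0.20/0.33/0.50 and C 0.20/0.33/0.50/0.60.

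| Assumed prior | A | B | C |
|---|---|---|---|
| MTD level 2, SD 1.16 | 3.4 | 2.1 | 1.1 |
| MTD level 3, SD 1.16 | 5.9 | 4.4 | 1.4 |
| MTD level 3, SD 0.5 | 7.5 | 12.0 | 17.7 |
| MTD level 4, SD 0.5 | 30.4 | 40.7 | 41.6 |

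Nearly all of these steps fall at the switch (for example 40.8 of the 41.6).

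**With a coherence restriction added,** the percentages become 0 by construction. In these cells mean DLTs move by at most 0.02 (for example 6.54 to 6.53). The largest change in patients treated above the MTD is 5.79 to 5.45. In a separate set (4 calibrations, 3 curves, 0.73 or 1.5 patients per month, 1500 trials per setting), 7% to 27% of trials had such a step. There the restriction changed mean DLTs by at most 0.1 and MTD selection by at most about 3 points, close to simulation error.

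**The case against.** **A safeguard applies to this very event.** Until the first DLT the dose only rises, so the current level is the highest opened, and any escalation at the switch opens a new one. That is when the DLT validation committee must be consulted. In a further 9 settings of 150 simulated trials, all 106 post-DLT escalations were to an unused level. A reader might infer from the restriction list that level 4 would open automatically for the next patient. The documents do not support that. What remains is that section 12.1.2 gives the committee no decision rule and no stated power to hold the dose.

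**Everything depends on a prior not yet fixed.** This stands, and it is why the result is a range. The planned calibration could avoid the problem. But its stated criterion is the expected number of toxicities, and that number barely differs with and without the restriction. A prior could therefore satisfy the criterion and still escalate after a DLT.

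**The rule is working as written, and little is gained.** In the worked example the level 4 estimate is 0.28, below target. The restriction binds one allocation only, after which escalation may go ahead. Both points are correct. They limit the benefit to the patient allocated directly after the DLT.

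**Conclusion.** The point holds as a gap in the allocation rule. With every written restriction met, the model can assign the next patient to a higher level directly after the DLT that triggers the switch. It does so under some priors and not others: 7 to 10 of 15 calibrations at level 3, 1 to 8 of 15 at level 2 and none at level 1 with variance 1.34. Simulated trials with such a step range from about 1% to 42%. All these figures rest on assumed skeletons, variances and true curves. They show what the rule permits and do not predict this trial.

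Two stronger readings should be resisted. One is that escalation after a DLT is likely, or has some fixed minimum frequency. With SD 1.16 the simulated range is only 1% to 6%, and without the skeleton and variance no single figure can be defended. The other is that the restriction would improve dose selection or reduce toxicity overall. The simulations show only small changes in either. This is an inexpensive improvement and does not invalidate the design.

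**What to change.** 1. Add one restriction to the list in the synopsis and in section 3.4.2: when a DLT has been reported since the last allocation, the model may not assign the next patient to a level above the last allocated one.
2. When the prior is calibrated, tabulate the model's first recommendation after the switch for a first DLT at each level, at minimum and at full follow-up. Confirm that none lies above the current level. This requires the skeleton and prior variance to be written down. The natural place is the SAP, whose 3+3 text has to be reconciled with the protocol in any case.

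The cost is one line in the rule and in its program, plus a short table. The downside is that occasionally one more patient is treated at the current level before escalation.

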	Unresectable tumors	Up to 59.4 Gy	1.8 Gy per fraction given once daily five days per week (Monday to Friday) over a period of 6.5 weeks.
Endpoints	PHASE I TRIAL: DOSE ESCALATION PART		
	Primary endpoint:		
	
 Toxicity graded using the common toxicity criteria from the NCI v4.0. Incidence rate of DLT at each dose level during treatment period up to six weeks after end of radiotherapy. 		
	Secondary endpoints		
	
 6-month non-progression is defined as CR, PR or stable disease (SD, more than 24 weeks) at 6 months according to RECIST 1.1. 6-month objective response is defined as CR or PR at 6 months according to RECIST 1.1. Best objective response under treatment is defined as complete (CR) and partial response (PR) recorded from the start of study treatment until the treatment with confirmation ≥ 4 weeks after initial documentation, as per RECIST 1.1. Objective response under treatment is determined once all the data for the patient is known. Best response under treatment is defined as the best response (CR, PR, SD) as per RECIST 1.1 recorded from the start of the study treatment until the end of treatment taking into account any requirement for confirmation as per RECIST v1.1 criteria. It is determined once all the data for the patient is known. 1-year Progression-free survival (PFS): PFS is defined as the time from study treatment initiation to the first occurrence of disease progression or death (of any cause), whichever occurs first. 1-year Overall Survival (OS): OS is defined as the time from study treatment initiation to death (of any cause). Functional assessment graded using the Musculoskeletal Tumour Society Rating Scale (Enneking, 1987). Pharmacokinetics (PK): PK measurements expressed as the AUC, the half-life of Olaparib and concentration peak. Pharmacodynamics (translational research): Predictive biomarkers analysis on available archived tumor tissue and mechanisms of action/pharmacodynamic activity on fresh biopsy (pre-treatment and week 4 of treatment). 		
	EXPANSION COHORT		
	Primary Endpoint		
	
 6-month non-progression is defined as CR, PR or stable disease (SD, more than 24 weeks) at 6 months according to RECIST 1.1. Disease status under treatment will be reviewed centrally by an expert radiologist. Reviewed data will be used for this primary endpoint analysis. 		

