ALT, alanine aminotransferase; ANC, absolute neutrophil count; AP, alkaline phosphatase; aPTT, activated partial thromboplastin time; AST, aspartate aminotransferase; ECG, electrocardiogram; ECOG PS, Eastern Cooperative Oncology Group Performance Status; INR, International Normalized Ratio; LDH, lactate dehydrogenase; MCH, mean cell haemoglobin; MCHC, mean cell haemoglobin concentration; MCV, mean cell volume; MRI, magnetic resonance imaging; RBC, red blood cell; RECIST v1.1, Response Evaluation Criteria In Solid Tumors; TP, prothrombin Rate; WBC,

	ASSESSMENT	TIME
--	------------	------

white blood cells.

5.5.EVALUATIONS DURING TREATMENT

The following assessments will be done while the patient is on treatment.

Table. Evaluations during treatment

	ASSESSMENT	TIME
1. Clinical examination	
 Complete physical examination Performance status (ECOG PS; see Appendix 1) Vital signs: heart rate, blood pressure, body temperature and weight 	
Repeat up to 48 hours before Day 1
 
Repeat on Day 1 of each subsequent week during radiotherapy: on Day 8, 15, 22, 29, 36, 43 and 50.
 
Repeat on week 10, 12, 14 and 24 thereafter in case of Olaparib discontinuation after the end of radiotherapy
 
Repeat on Day 1 of each subsequent month in case of Olaparib continuation after the end of radiotherapy.

	
 Assessment of baseline signs and symptoms 	Throughout the treatment period
	
 Concomitant diseases and treatments 	Throughout the treatment period
	
 Functional assessment MSTs 	Completed by the radiotherapist at baseline and at the end of radiotherapy treatment

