2. Laboratory tests*	
 Hematology: differential WBC, ANC, haemoglobin, platelets, RBC, MCV, MCHC, MCH Biochemistry: Serum electrolytes (Na⁺, K⁺, Mg⁺⁺ and Ca⁺⁺), liver function tests (AST, ALT, total bilirubin, GGT and AP), LDH, creatinine, fasting glucose, total proteins, urea, albumin Coagulation: TP, INR, aPTT, if clinically indicated Urinary: dipstick if clinically indicated 	
Repeat up to 48 hours before Day 1
 
Repeat every two weeks, on Days 15, 29 and 43
 
Repeat on week 10, 12, 14 and 24 thereafter in case of Olaparib discontinuation after the end of radiotherapy
 
Repeat on Day 1 of each subsequent month in case of Olaparib continuation after the end of radiotherapy.
 
 If clinically indicated
3. Creatinine clearance	
 Calculated according local institution (see Appendix 2) 	
Repeat up to 48 hours before Day 1
 
Repeat every two weeks, on Days 15, 29 and 43
 
Repeat on week 10, 12, 14 and 24 thereafter in case of Olaparib discontinuation after the end of radiotherapy
 
Repeat on Day 1 of each subsequent month in case of Olaparib continuation after the end of radiotherapy.

4. Pregnancy test, if applicable	
 Measurement of serum human chorionic gonadotropin (HCG) 	
On day 1 prior to the start of study treatment.
 
In the event of a suspected pregnancy during the study, the test should be repeated.

5. ECG	
 QTc measurement: twelve-lead ECGs will be obtained after the patient has been rested in a supine position for at least 5 minutes. ECGs will be recorded at 25 mm/sec. 	
At week 10
 
 If clinically indicated
6. Tumor assessment	
 MRI of all measurable sites, as per RECIST (see Appendix 3) CT Scan only for patients with metastatic disease 	
Tumor assessment must be repeated
 
 MRI: every twelve weeks (±7 days) and at least four weeks after first documentation of objective response even if there are treatment delays: on weeks 12 and 24. CT Scan: every 8 weeks.
7. PK study	
 Blood samples 	See section 17.1.1
8. Optional biopsy	
 Predictive markers of treatment outcome from tumor samples 	See section 17.2.1

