7.2.5. Adverse effects management

Acute toxicities of radiotherapy of STS are essentially musculoskeletal or cutaneous toxicities. They will be evaluated through a clinical examination performed each week during radiotherapy and one month after the end of radiotherapy (D8, D15, D22, D29, D36, D43, D50, D64, D78, D92) or until regression of a grade 3. Grading of adverse events will be done according to the CTCAE v.4.

- If a grade ≥ 3 musculoskeletal or cutaneous toxicity is observed before a radiotherapy dose of 30Gy, Olaparib and radiotherapy were stopped (DLT) but radiotherapy could be continued when regression to a grade ≤ 2 will be achieved.
- If a grade ≥ 3 musculoskeletal or cutaneous toxicity is observed after a radiotherapy dose of 30Gy, radiotherapy will be stopped until regression to a grade ≤ 2 and then will be continued. Olaparib will be continued during radiotherapy interruption. If grade ≥ 3 persits more than 4 weeks, Olaparib will be stopped (DLT).

The irradiated skin area that will be included in the operative volume must be identified during contouring and protected during planification (ALARA) in order to limit the occurrence of post-operative acute cutaneous and mucous complications [30 - 31].

7.3.ASSOCIATED TREATMENT: SURGERY FOR RESECTABLE DISEASE

Surgery will be performed by expert surgeon within 12 weeks of radiotherapy completion in reference centers labelled by the French NCI and NETSARC network.

Post-operative complications will be recorded up to 12 months after surgical complication.

Surgical sample will be analyzed to determine histological response and data will be collected in case report form.

The decision of surgery has to be taken by the investigational site during Multidisciplinary Tumor Board (RCP),

The decision of surgery has to be notified to the sponsor as soon as possible (i.e. before surgery).

Post-surgery clinical exam: addition of 3 visits after surgery (D30, D60 and D90). The next visits remain unchanged (follow-up every 3 months).

Post-surgery complications grade 3 should be reported immediately as serious adverse event to the Vigilance Unit of the Sponsor.

CONFIDENTIAL

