 - For the upper limb: the position relative to shoulder, dexterity, muscle strength
 - Each criterion is evaluated with a question (eg, pain is assessed by the consumption of analgesic drugs). The evaluation of each test contains six levels of achievement or scores, four defined scores (0, 1, 3, 5) and two intermediate (2, 4). The four scores are defined the score 5: absence of impact; the score 3: minor impact; the score 1: major repercussions; the score 0: disability.
- Concerning the analysis of MSTS,
 - The total score will be described at each measurement time
 - A difference of 10 points or more will be used to define a clinically significant difference. There is particular focus on the difference between the observed scores before surgery and 1 year post surgery.
- PK measurements expressed as AUC, half-life and concentration peak for Olaparib.

9.2.EXPANSION COHORT

Primary endpoint

6-month non progression as defined for the dose escalation part. For the expansion cohort, radiological data will be centrally reviewed. The primary analysis will be based on reviewed data.

Secondary endpoints

- Antitumor activity observed with Olaparib given in association with radiotherapy in terms of 6-month objective response, best response under treatment, best objective response under treatment, 1-year PFS and 1-year OS, as defined for the dose escalation part.
- Toxicity graded using the common toxicity criteria from the NCI v4.03.
- PK measurements expressed as AUC, half-life and concentration peak for Olaparib.
- Pharmacodynamics (translational research): Prognostic markers of anti-tumor activity of Olaparib given with concomitant radiotherapy will be investigated.

10.STATISTICAL CONSIDERATIONS

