### 3.2.1.2 EXPANSION COHORT

6-month non progression, defined as complete (CR) or partial response (PR) at 6 months confirmed  $\geq 4$  weeks after initial documentation, or stable disease more than 24 weeks (RECIST v1.1, as determined by investigator review of tumor assessments).

For the expansion cohort, radiological data will be centrally reviewed. The primary analysis will be based on reviewed data.

Criteria	eFORM variable	Control
6-month non progression	TUM_CYC (TUMOR ASSESSMENT) DT_MEAC (date of measurement) ME1L_ME5L (measures of lesions) SUM_TL (largest diameters) EVA1LNM_EVA5LNM (non-measurable lesions eval) RES_TL, RES_NTL (target and non-target lesions) OV_RESP (overall response) CR=1, PR=2, SD=3 TRT_OLA DT_S10 (D1 Olaparib)	DT_S10 filled in ME1L_ME5L (filled in if needed) SUM_TL filled in EVA1LNM_EVA5LNM (filled in if needed) RES_TL, RES_NTL (filled in) and check recist1.1 criteria  check for each patient (( DT_MEAC-DT_S10 $\geq 6$ ) and OV_RESP =(1 or 2 or 3)) Count number of non-progression case

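### The week-24 MRI meant to supply the 6-month result does not fit the SD condition of the primary endpoint, and the SAP's date rule singles out that scan under no unit

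*Protocol*

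**What the plan says.** The protocol synopsis (Endpoints, expansion cohort) gives the primary endpoint: "6-month non-progression is defined as CR, PR or stable disease (SD, more than 24 weeks) at 6 months according to RECIST 1.1". Protocol 9.1, which 9.2 adopts for the expansion cohort, adds that CR and PR must be confirmed at least 4 weeks after they are first documented.

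The imaging schedule is in protocol 5.5: "MRI: every twelve weeks (±7 days) and at least four weeks after first documentation of objective response", with weeks 12 and 24 named as the visits. Patients with metastatic disease also have CT every 8 weeks. Protocol 8.2.2.1 has the central reviewer judge 6-month status from the baseline, week-12 and week-24 images, so week 24 is the intended 6-month assessment.

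On the reader, protocol 9.2 says: "For the expansion cohort, radiological data will be centrally reviewed. The primary analysis will be based on reviewed data". SAP 3.2.1.2 repeats this, but only after a definition that ends "or stable disease more than 24 weeks (RECIST v1.1, as determined by investigator review of tumor assessments".

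The SAP 3.2.1.2 control requires DT_MEAC minus DT_S10 (scan date minus first olaparib date) to be at least 6, with the overall response OV_RESP coded "1 or 2 or 3)) Count number of non-progression case". The codes are CR, PR and SD.

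**The concern.** The endpoint text, the scan schedule and the programmed rule should all point to one scan and one reading of it. They do not. The SD threshold lies at or beyond the end of the window of the scan that is meant to establish SD. The SAP rule does not name that scan, and its threshold of 6 has no unit.

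Non-progression includes SD, so the timing rule for SD bears directly on the result. Under the literal SD text, a patient with stable disease on an on-time week-24 scan may not count. Under a loose reading of the SAP rule, a patient who is stable at week 12 and progresses by week 24 may count. Two programmers following SAP 3.2.1.2 could report different primary results from the same data.

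**Working it through.** **Plan's own figure.** Protocol 10.1 uses the first stage of a Gehan design with a 20% efficacy rate and a 5% error. The smallest n with 0.8^n ≤ 0.05 is 14, since 0.8^13 = 0.0550 and 0.8^14 = 0.0440. The stated 14 is reproduced and is not in question.

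**Day of week 24.** Protocol 5.5 numbers the weekly visits "Repeat on Day 1 of each subsequent week during radiotherapy: on Day 8, 15, 22, 29, 36, 43 and 50", and 7.2.5 continues "D8, D15, D22, D29, D36, D43, D50, D64, D78, D92". Matched with the schedule table, week k starts on Day 7(k−1)+1: week 8 is Day 50, week 10 Day 64, week 12 Day 78, week 14 Day 92. The table prints no day for week 24; the same formula gives 7×23+1 = Day 162.

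**Window on that numbering.**
- Time from first dose: 162−1 = 161 days = 23.0 weeks.
- With ±7 days: 154–168 days = 22.0–24.0 weeks = 5.06–5.52 months (30.4375 days per month).
- SD needs more than 24×7 = 168 days. The last in-window day gives exactly 168, so the condition is not met.
- Six calendar months is 6×30.4375 = 182.6 days, also not met.

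**Window if week 24 means 24 completed weeks.**
- 168±7 = 161–175 days = 23.0–25.0 weeks = 5.29–5.75 months.
- The nominal scan is at exactly 24.0 weeks and does not qualify. Scans at 169–175 days do. None reaches 182.6 days.

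**SAP rule, by unit.**
- *Months:* every in-window week-24 scan fails (at most 5.52, or 5.75 on the second numbering), and a later scan has to be used.
- *Weeks:* the week-8 CT (49/7 = 7.0), the week-12 MRI (77/7 = 11.0) and the week-24 MRI (23.0) all pass.
- *Days:* all scheduled post-baseline scans pass, including week 12 at 77 days.

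No unit singles out week 24. The rule also has no upper limit and does not exclude a patient with PD at an earlier visit.

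**Which later scan, if months.** The anchor of the 3-monthly follow-up is not stated consistently enough to fix one answer. Taking 3 months as 91 days:
- counted from the end of the treatment period (Day 52 plus 6 weeks): 51+42+91 = 184 days = 6.05 months;
- week-32 CT, metastatic patients: 217 days = 7.1 months;
- counted from week 24: 161+91 = 252 days = 8.3 months.

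**Reader and confirmation.** SAP 3.2.1.2 lists TUM_CYC and OV_RESP for the centrally reviewed expansion endpoint. SAP 3.2.2.1 lists the same form and fields for the investigator-assessed escalation endpoint. No central-review field appears in either. The 3.2.2.1 control includes the 4-week confirmation check; the 3.2.1.2 control does not, although the definition above it requires confirmation.

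**Consequence.** One patient is 1/14 = 7.1 percentage points. Protocol 10.1 calls the combination worthy of further testing if at least one of 14 is a non-progression. Assuming that rule counts the primary endpoint, the probability of passing is 1−(1−p)^14: 0.956 at the planned 20%, and 0.77 and 0.51 at assumed true rates of 10% and 5%. One reclassified patient changes the decision when no other patient counts as a success.

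**The case against.** Several points can fairly be made in the plan's defence.

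- *Day 162 is extrapolated.* The MRI row says "MRI: every twelve weeks (±7 days", which can be read as 168±7 days, and scans on days 169–175 then satisfy the SD condition. This stands. A reader might infer that no in-window scan can ever qualify; the documents do not support that on this reading.
- *The origin for SD duration is not stated.* Baseline imaging may precede Day 1 by up to four weeks, with one further week of tolerance. Timed from that scan, week 24 can exceed 24 weeks. This stands, and it is itself a gap.
- *Week 24 is plainly the intended 6-month visit* (protocol 8.2.2.1), so a 183-day test holds the label to a precision the protocol does not use. This stands for the intent. It does not help the SAP rule, which applies a numerical 6 and, in months, excludes that visit.
- *SAP controls usually take their unit from the criterion:* years for age, days for the pregnancy test, weeks for prior therapy. Months is therefore the natural reading of a row headed 6-month non-progression. Agreed, but months is the reading that rejects every in-window week-24 scan.
- *The primary analysis is on centrally reviewed data.* A reader might infer that the SAP uses the investigator's reading. It does not say so: the sentence after the investigator wording specifies reviewed data, and protocol 8.2.2.1 lets the expert prevail when readings differ. What remains is a self-contradiction and the absence of a named central-review variable.
- *The analysis is descriptive, without p-values.* True, but the estimated rate and the one-in-14 rule both depend on which patients count.

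**Conclusion.** The point holds in this form. On the schedule's numbering and counting from first dose, on-time SD at week 24 (154–168 days) does not meet the endpoint text. If week 24 means 168±7 days, only scans 1–7 days late meet it. Neither reading reaches six calendar months. CR and PR are untouched by the 24-week condition.

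The SAP defect does not depend on the numbering: no unit makes the rule select the week-24 scan. In months it moves to a scan at about 6 to 8.3 months; in days or weeks it also admits week 12. A reader might infer a bias in one direction, or a fixed delay of about three months. Neither follows, because the unit and the follow-up anchor are both unstated.

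A rule for the primary endpoint that gives a wrong result if followed as written needs correction before analysis.

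**What to change.** In the protocol synopsis, protocol 9.1/9.2 and SAP 3.2.1.2:

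- Define the 6-month assessment as the week-24 scan. State the origin (DT_S10), the unit (days) and a window that contains the scheduled scan and its ±7 days: 154–168 days on the schedule's numbering, or 161–175 if week 24 is declared to be 168 days.
- Set the SD minimum at the lower end of that window, so that on-time SD counts.
- Require CR, PR or SD on central review at that assessment. Count PD or death at or before it as failure.
- Keep the rule in protocol 10.2 and SAP 2.1.2 that eligible patients withdrawn for the listed reasons without any tumour assessment are failures.
- State how a missing week-24 scan is classified. A patient with only a week-12 scan is assessable under those sections but has no defined outcome, and missing data are not imputed.
- Replace OV_RESP with a named central-review response variable, remove the investigator wording for the expansion cohort, and add the 4-week confirmation check.
- Report the investigator reading as a sensitivity analysis.

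The cost is wording and programming. No scans are added, since protocol 8.2.1 already requires repeat imaging to confirm a response. The one concession is an SD minimum slightly below 24 weeks.
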